5.5.1 Primary efficacy endpoint(s)

The primary efficacy endpoint is the change from baseline to Week 8 of DB treatment period (Period II) in mean trough (i.e., 24 hours post-dose) SiDBP, measured by OBPM.

Baseline is defined as described in Section 5. Week 8 is the time window of Visit 7 [Section 11.1].

SiDBP is retrieved from the SDTM VS domain selecting VSTESTCD="DIABP" and VSSCAT='Average'.

5.5.2 Secondary efficacy endpoints

- Change from baseline to Week 8 of DB treatment period (Period II) in mean trough SiSBP, measured by OBPM and collected as described for SiDBP.
 - SiSBP is retrieved from the SDTM VS domain selecting VSTESTCD="SYSBP" and VSSCAT='Average'.
- Control and response status at Week 8 of DB treatment period (Period II) based on trough SiDBP, measured by OBPM;
 - Controlled, if mean SiDBP < 90 mmHg;
 - Responder, if the reduction from baseline in mean SiDBP ≥ 10 mmHg;
 - Controlled according to CHEP guidelines [Leung 2016], if mean SiDBP < 85 mmHg.
- Control and response status at Week 8 of DB treatment period (Period II) based on trough SiSBP, measured by OBPM;
 - Controlled, if mean SiSBP < 140 mmHg;
 - Responder, if the reduction from baseline in mean SiSBP ≥ 20 mmHg;
 - Controlled according to CHEP guidelines [Leung 2016], if mean SiSBP < 135 mmHg.
- Change from baseline to Week 8 of DB treatment period (Period II) in 24-hour mean DBP, measured by ABPM;
 - ABPM will be measured before start of treatment (Day -1, Visit 4) and after the last dose (Day 55, Visit 7). At each visit the 24-hour mean DBP will be derived from the area under the DBP-time curve, divided by the time span. [See Figure 1 for clarification.] Time points later than 25 hours after the first time point will be excluded from the calculation. The change from baseline to Week 8 will be obtained as the difference in 24-hour mean DBP ABPM between Visit 7 and Visit 1.
- Change from baseline to Week 8 of DB treatment period (Period II) in 24-hour mean SBP, measured by ABPM;
 - The change from baseline to Week 8 will be obtained as the difference in 24-hour mean SBP ABPM between Visit 7 and Visit 1, where the 24-hour mean SBP ABPM is calculated similar to the 24-hour mean DBP ABPM.

- Trough to peak ratio for DBP based on ABPM.
 - The trough to peak ratio will be derived on treatment group level [FDA 2007] based on the time course of ABPM and will be corrected for baseline according to the following steps:
 - Patient level: for each visit (Visit 4 / Day -1 and Visit 7 / Part 1) the patient's ABPM-DBP will be averaged by hour after drug intake (0, 1, ..., 24), applying a window of 30 minutes around each hour (lower limit excluded; upper limit included).
 - Group level: for each visit (Visit 4 / Day -1 and Visit 7 / Part 1) and hour after drug intake (0, 1, ..., 24) the ABPM-DBP will be averaged by treatment group.
 - Group level: for each hour after drug intake (0, 1, ..., 24) and the treatment group the difference in mean ABPM-DBP between Week 8 (Visit 7 Part 1) and baseline (Visit 4 Part 1) will be obtained.
 - Group level: the trough to peak ratio will be calculated as the average of the (five) differences at hours 20–24 (expected trough) divided by the average of the (five) differences at hours 2–6 (expected peak at 4 hours \pm 2 hours) [See Appendix C for illustration.]

Baseline is defined as described in Section 5 and Week 8 is the time window of Visit 7 [Section 11.1].

In the evaluation of changes from baseline and control/response status, only subjects with both the baseline and the time point assessments available will be included.

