7.2.3 Ambulatory blood pressure monitoring

Two 24-h ABPMs will be performed:

- Baseline ABPM: At the end of the SB placebo run-in period; 24 h before Day 1 (Visit 4 / Randomization).
- End of DB treatment ABPM: At the end of the DB treatment period; 24 h after Visit 7 / Part 1.

Essential hypertension Protocol AC-080A201 Version 3 30 May 2016, page 59/112

Confidential

The ABPM device (Mobil-o-Graph) will be provided to each site by the central BP laboratory for the duration of the study.

ABPM is performed over a 24-h period with the ABPM device set to record BP at a predefined inflation sequence over the 24-h period.

ABPM data will be electronically transferred to the central BP laboratory and subsequently to Actelion.

Details on ABPM procedure (installation, recording and transfer of data) including subject preparation will be provided in the BP laboratory manual.

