5.5 Efficacy variables

All efficacy data are collected electronically and are transferred to Actelion by [REDACTED].

OBPM, SiDBP and SiSBP (mmHg) are measured at the study site by the BpTRU[®] device using six measurements per subject / visit. These measurements and their average (excluding the first measurement) are uploaded into the [REDACTED] database. The data

transfer from [REDACTED] to Actelion includes the separate measurements as well as the average which will be used as the subject's SiDBP or SiSBP value for that visit. The average will not be re-calculated by the sponsor. The sponsor will perform spot checks to confirm that the average was been correctly calculated [REDACTED]

ABPM is performed over a 24-h period with the ABPM device set to record DBP and SBP at a pre-defined inflation sequence over the 24-h period including three measurements per hour during the day and two per hour during the night. ABPM data are electronically transferred to [REDACTED] and subsequently to Actelion. The [REDACTED] supplements each ABPM reading with an indicator of whether the reading satisfied the quality control criteria agreed between [REDACTED] and Actelion [REDACTED]

1. Start time of ABPM is between 06:00 and 11:00
2. Duration of ABPM is at least 24 hours
3. Percentage of valid readings in the period of duration is at least 75%
4. Number of required hours (i.e., hours with at least one reading) is at least 22
5. Number of exception hours (i.e., hours without a reading) is at most 2
6. No two consecutive exception hours

In addition, there is an indicator (Y/N) for the overall quality of the ABPM reading. This is only set to Y if all six criteria are met.

It should be noted that when an ABPM reading does not satisfy all 6 criteria, this does not necessarily mean that this reading should be excluded from the analysis as the ABPM analysis primarily focuses on the 24 hour means [REDACTED]. For the analysis of 24 hour means, criteria 3 and 6 are considered to be the most relevant ones by Actelion.

For this reason, the ABPM analyses will be based on the subset of subjects from the PPS with baseline and Week 8 ABPM readings satisfying quality criteria 3 and 6 (i.e., ABPM readings having less than 75% valid readings and/or two consecutive exception hours will be excluded). As this subset is likely to be comprised of < 50% of subjects, formal dose-response analyses for the ABPM endpoints will be carried out as needed.

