5.5.3 Other efficacy endpoints

- Changes from baseline to time window Visit 5 (Week 2) and time window Visit 6 (Week 4) of DB treatment period (Period II) in mean trough SiSBP and SiDBP (measured by OBPM);
- Change from baseline to Week 8 of DB treatment period (Period II) in mean daytime ABPM;
 - *Change from baseline in mean daytime DBP.* All ABPM measurements taken between 09:00 and 21:00 will be included in this calculation [O'Brien 2013]; there may be two parts of the daytime DBP-time curve to be considered for a subject at a given visit, one for each calendar day of Visits 4 and 7. At each visit the mean daytime DBP will be derived from the area under the DBP-time curve(s), divided by the time span(s) [see Appendix B for clarification]. The change from baseline to Week 8 will be obtained as the difference in mean daytime DBP ABPM between Visit 7 and Visit 4.
 - *Change from baseline in mean daytime SBP.* Similar to change from baseline in mean daytime DBP.

[figure not shown]
- Change from baseline to Week 8 of DB treatment period (Period II) in mean night time ABPM;
 - *Change from baseline in mean night time DBP.* All ABPM measurements taken between 01:00 and 06:00 will be included in this calculation [O'Brien 2013]; there should be one night time part of the DBP-time curve to be considered for each subject at a given visit; in the unlikely event that there are two, only the first one will be used). At each visit the mean night time DBP will be derived from the area under the DBP-time curve, divided by the time span [see Appendix B for further specification]. The change from baseline to Week 8 will be obtained as the difference in mean daytime DBP ABPM between Visit 7 and Visit 4.
 - *Change from baseline in mean night time SBP.* Similar to change from baseline in mean night time DBP.
- Trough to peak ratio for SBP based on ABPM;
 - The trough to peak ratio for SBP will be derived on treatment group level based on the time course of ABPM as similar to the trough to peak ratio for DBP.
- Changes from baseline to time window Visit 8 (Week 10 i.e., Week 2 of withdrawal period - Period III) in mean trough SiSBP and SiDBP (measured by OBPM);
- Changes from Week 8 of Period II to time window Visit 8 (Week 10 i.e., Week 2 of withdrawal period - Period III) in mean trough SiSBP and SiDBP (measured by OBPM).

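### Two ABPM endpoint rules in the SAP name the wrong input: the 24-hour changes use Visit 1, where no ABPM is recorded, and the night-time change is defined from daytime means

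*SAP*

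**What the plan says.** Protocol 7.2.3: "Two 24-h ABPMs will be performed". The first is described as "Baseline ABPM: At the end of the SB placebo run-in period; 24 h before Day 1", which is Visit 4; the second starts at Visit 7 / Part 1. Section 5 of the SAP agrees: it places the ABPM baseline between the last run-in placebo dose and the first double-blind dose.

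SAP 5.5.2, on the 24-hour means, opens consistently with this: "ABPM will be measured before start of treatment (Day -1, Visit 4) and after the last dose (Day 55, Visit 7"). The same bullet then defines the change as "the difference in 24-hour mean DBP ABPM between Visit 7 and Visit 1", and the SBP bullet as "the difference in 24-hour mean SBP ABPM between Visit 7 and Visit 1". The section closes by referring back to Section 5 for baseline and by limiting change analyses to subjects who have both assessments.

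SAP 5.5.3, on day and night means, has this sentence in the daytime DBP rule: "The change from baseline to Week 8 will be obtained as the difference in mean daytime DBP ABPM between Visit 7 and Visit 4". It is correct there. The same sentence ends the night-time DBP rule, after a mean over 01:00 to 06:00 has been derived. Night-time SBP is defined only as similar to night-time DBP.

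SAP 5.5 lists six quality criteria for a recording and uses two of them, 3 and 6, to select recordings: "ABPM readings having less than 75% valid readings and/or two consecutive exception hours will be excluded". Criterion 3 reads "Percentage of valid readings in the period of duration is at least 75" per cent.

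**The concern.** These sentences are the operative derivation rules that a programmer would follow. The 24-hour ABPM response is part of a stated secondary objective, and the 24-hour DBP ANCOVA outputs in SAP 13.7 are marked as key, meaning that they feed the initial reading of dose-response.

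The two slips would fail differently. The Visit 1 rule fails visibly, because there is nothing to subtract. The night-time rule runs without error and returns plausible numbers, which are the daytime changes under a night-time label. The second kind is harder to catch in output review.

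A smaller question sits beside these. The 24-hour mean is the area under the curve divided by the recording's own time span. The calculation has an upper cut-off of 25 hours but states no minimum length.

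**Working it through.** **1. The SAP's worked example reproduces (5.5.3.1 and Appendix B).** The recording runs from 10:29 to 11:04 the next day, 24 h 35 min = 88,500 s.
- 24-hour mean: DBP 8,640,870 / 88,500 = 97.6; SBP 12,956,970 / 88,500 = 146.4.
- Daytime mean: DBP (3,705,300 + 801,570) / (37,860 + 7,440) = 99.5; SBP (5,224,530 + 1,295,970) / 45,300 = 143.9.
- Night-time mean: DBP 1,411,200 / 18,000 = 78.4; SBP 2,438,100 / 18,000 = 135.5.

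All six agree with the SAP, so the averaging rule is sound. The example covers means at one visit and never forms a change, so it does not correct the faulty sentences.

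**2. The 24-hour rule applied literally.** Recordings exist at Visit 4 and Visit 7 only. Visit re-mapping does not help: in SAP Table 5 the Visit 1 window ends at Day -35, while Day -1 falls in the Visit 4 window (Day -3 to Day 1). If Visit 1 is taken as the baseline visit, no subject has both assessments, so n = 0. With Visit 4, every subject with two usable recordings has a value.

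**3. The night-time rule applied literally.** Night-time DBP change = daytime mean at Visit 7 minus daytime mean at Visit 4, which is the daytime endpoint. SBP inherits this. Yet SAP 10.8, Table 4 and the output list in 13.8 treat day and night as separate analyses. In the example the two means are different quantities: 99.5 - 78.4 = 21.1 mmHg for DBP and 143.9 - 135.5, or 8.5 mmHg before rounding, for SBP.

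**4. Recording length: two readings of criteria 3 and 6.**
- *Judged over the recorded period.* No minimum length follows. The example stopped at 21:00 (10 h 31 min) could pass, giving DBP 3,705,300 / 37,860 = 97.9 (+0.2 before rounding) and SBP 5,224,530 / 37,860 = 138.0 (-8.4).
- *Judged over a nominal 24 hours.* Criterion 6 bars two consecutive hours without a reading, so the last reading must fall in hour 23 or 24, an implicit minimum above 22 hours. The recording stopped at 21:00 fails. It also fails criterion 3. With three readings an hour by day and two by night, and an assumed night schedule of 6 to 9 hours (the documents give no length), 66 to 63 readings are scheduled. About 31 fall in 10.5 daytime hours, and 31/66 to 31/63 is 47% to 49%, below 75%.

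**The case against.** The strongest reply is that nobody would be misled. The 24-hour bullet itself names Visit 4, Section 5 fixes the ABPM baseline, the daytime and trough-to-peak rules use Visit 4, and only one pre-treatment recording exists. Likewise the night mean is derived correctly and analysed separately. All of this is true, and it makes the intent clear. SAP 10.1 also treats every analysis other than the main one as exploratory. This limits the importance of the point, but the rules still contradict the rest of the plan and cost almost nothing to correct.

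A reader might infer more than the documents support.
- *That the 21.1 mmHg gap is the size of the night-time error.* It is a difference in level in one subject at one visit. The slip would swap one change for another, and the documents do not show how far day and night changes differ.
- *That short recordings add an error as large as the drug effect.* Using criteria 3 and 6 alone is a disclosed choice with a stated reason. Text around the agreed criteria is redacted, so the hour-counting rule may be there. Criteria 4 and 5 (22 hours with a reading, at most 2 without) add up to 24, which suggests a nominal 24 hours, under which early-stopped recordings are excluded. No frequency of short recordings is given, and the -8.4 above is SBP in one subject.
- *That losing the night shifts DBP by 4.9 mmHg.* The arithmetic (8,640,870 - 1,411,200) / (88,500 - 18,000) = 102.5, against 97.6, describes a five-hour hole. Criterion 6 excludes such a recording, and the trapezoidal rule would bridge the gap rather than delete it. The 4 mmHg benchmark in SAP 10.6.3 is a placebo-corrected group mean for office DBP, which is not comparable.

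**Conclusion.** The point holds as a correction to two rules. The 24-hour DBP and SBP changes refer to a visit with no ABPM, and the night-time DBP change, with SBP by reference, is defined from the wrong means. This rests on the text alone and needs no numerical assumption. Its reach is four ABPM endpoints. The primary endpoint, its MCP-Mod test, the sample size and the trough-to-peak ratios, which already use Visit 4, are untouched. The slips do not show that the endpoints would in practice be uncomputable or misreported, because the intended derivation can be recovered from other sections.

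On recording length only a clarification is warranted: the visible text does not say over which period criteria 3 and 6 are judged. It does not establish that short recordings are admitted, or that they would bias the result by any stated amount.

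**What to change.** - SAP 5.5.2: replace Visit 1 with Visit 4 in the 24-hour DBP bullet and in the 24-hour SBP bullet.
- SAP 5.5.3: in the last sentence of the night-time DBP rule, replace daytime with night time. The SBP rule then follows correctly.
- SAP 5.5 (and 4.1.2, where the criteria are repeated): add one sentence stating whether criteria 3 and 6 are judged over a nominal 24 hours or over the recorded period.

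The cost is three wording changes and one sentence, plus a check that the derivation programs match. No data, model or output changes. Adding criterion 4 as a further filter is not requested: SAP 5.5 already expects fewer than half of subjects in the ABPM subset, and another exclusion would be a trade-off rather than a correction.

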For this reason, the ABPM analyses will be based on the subset of subjects from the Per-Protocol Set (PPS) with baseline and Week 8 ABPM readings satisfying quality criteria 3 and 6 (i.e., ABPM readings having less than 75% valid readings and/or two consecutive exception hours will be excluded).

Trough to peak ratios based on ABPM. In the protocol it was assumed that trough to peak ratios of DBP and SBP measured by ABPM would be derived on a subject level. However, the definition of subject-specific trough to peak ratios [Omboni 1995] appears to be problematic because of individual ABPM variation over time. Based on clinical rationale and following the reasoning in recent FDA reviews such as FDA 2007, the trough to peak ratios of DBP (and SBP) were re-defined on a treatment group level based on the time course of the 24 hours ABPM. As a consequence, the analysis in the protocol (which assumed a definition on a subject level) was replaced by descriptive statistics [Section 10.7].

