10.2 General rules for data presentations

This section describes the general rules applied for all data displays.

SAS version 9.3 is used for the statistical analyses except for the primary endpoint (dose-response analysis) that is analyzed by means of the R package.

Unless otherwise specified in this document:

- All listings are sorted by randomized treatment, subject number and, when appropriate, by visit / date of assessment. If a listing includes non-randomized subjects, these will appear after the randomized subjects. All data collected are displayed, including unscheduled visits (if any).
- In summary tables and graphical representations, subjects are grouped by randomized treatment group, except for the SAF for which the actual treatment is used.
- In summary tables based on the RND, FAS, PPS and SAF, the order of the treatment groups is: placebo, ACT-132577 5 mg, ACT-132577 10 mg, ACT-132577 25 mg, ACT-132577 50 mg and Lisinpril 20 mg, followed by Total (if required). In summary tables based on the RIS or SCR, only a total column will be given.

- The absolute change from baseline to Visit X is defined as the difference between the post-baseline Visit X value and the baseline value.
- In order to analyze the data at the relevant planned (scheduled) visits, all recorded assessments for each subject up to the Week 10 visit are reassigned to the most appropriate visit according to the time window for that visit. The windows are consecutive (i.e., there are no gaps) and are based on the study day corresponding to the date of assessment. Any unscheduled visit is also mapped to a time window. Details of the visit mapping are given in Section 11.1.
- According to section 11.3.2.2 of the protocol, imputation rules for missing data are defined for the evaluation of efficacy endpoints at Week 8. Subjects without a value in the defined Week 8 time window are included in the analysis according to the rules highlighted in Section 9.

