10.7 Analysis of the secondary efficacy variables

Secondary efficacy variables will be analyzed for the PPS at $\alpha = 0.05$ (two-sided) using 95% CIs. Additionally, change from baseline to Week 8 in mean trough SiSBP will be analyzed for the FAS. No correction for multiple testing will be applied for these analyses.

Change from baseline to Week 8 of DB treatment period (Period II) in mean trough SiSBP will be analyzed similarly to the primary endpoint (SiDBP), i.e., MCP-Mod will be applied, supplemented by the ANCOVA and the repeated measurements models described above. The correlation between the changes from baseline in SiDBP and SiSBP will be displayed in a scatter plot for each post-baseline time point.

Control (< 90 mmHg and < 85 mmHg, separately) and response (Y/N) at Week 8 of DB treatment period (Period II) based on trough SiDBP will be analyzed using a logistic regression model with a factor for treatment group and a covariate for baseline mean trough SiDBP. Control and response status at Week 8 of Period II based on trough SiSBP will be analyzed similarly.

Change from baseline to Week 8 of DB treatment period (Period II) in 24-hour mean DBP based on ABPM will be analyzed using an ANCOVA with a factor for treatment group and a covariate for baseline 24-hour mean DBP. Change from baseline to Week 8 of DB treatment period (Period II) in 24-hour mean SBP based on ABPM will be analyzed similarly.

The baseline and Week 8 average ABPM-DBP curves over time (by hour) will be plotted by treatment group [averaging as described in Section 5.5.2]. Additionally, the Week 8 minus baseline difference will be plotted vs time. Trough to peak ratios for DBP will be calculated by treatment group as described in Section 5.5.2.

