24H_DBP_AN COVA	T	ANCOVA for change from baseline to Week 8 in 24-hour mean diastolic blood pressure (DBP) as measured by ABPM - ACT-132577 vs Placebo	PPS	Yes	LAYBETW00 1

Output name	Display *	Title (Description)	Analysis set(s)	Key	Mock layout
24H_DBP_ANCOVA_L	T	ANCOVA for change from baseline to Week 8 in 24-hour mean diastolic blood pressure (DBP) as measured by ABPM - Lisinopril vs Placebo	PPS	Yes	LAYBETW001
24H_SBP_CHG	T	Change from baseline to Week 8 in 24-hour mean systolic blood pressure (SBP) as measured by ABPM by treatment group	PPS		LAYBASE001
24H_SBP_ANCOVA_L	T	ANCOVA for change from baseline to Week 8 in 24-hour mean systolic blood pressure (SBP) as measured by ABPM - Lisinopril vs Placebo	PPS	Yes	LAYBETW001
OBPM	L	Listing of mean trough sitting diastolic (SiDBP), mean trough sitting systolic blood pressure (SiSBP) and pulse rate measured by OBPM with control and response rates	FAS		L_OBPM
ABPM24_DBP_BAS	F	Mean diastolic blood pressure (DBP) per hour as measured by ABPM at baseline	PPS		LAY_ABPM
ABPM24_DBP_WK8	F	Mean diastolic blood pressure (DBP) per hour as measured by ABPM at Week 8	PPS		LAY_ABPM

Output name	Display *	Title (Description)	Analysis set(s)	Key	Mock layout
ABPM24_DBP_WK8_DIF	F	Difference in mean diastolic blood pressure (DBP) per hour as measured by ABPM	PPS		LAY_ABPM
ABPM24_DBP_TTPR	T	Trough to peak ratio for diastolic blood pressure (DBP) measured by ABPM	PPS		LAY_TTPR
ABPM24_SBP_BAS	F	Mean systolic blood pressure (SBP) per hour as measured by ABPM at baseline	PPS		LAY_ABPM
ABPM24_SBP_WK8	F	Mean systolic blood pressure (SBP) per hour as measured by ABPM at Week 8	PPS		LAY_ABPM
ABPM24_SBP_WK8_DIF	F	Difference in mean systolic blood pressure (SBP) per hour as measured by ABPM	PPS		LAY_ABPM
ABPM24_SBP_TTPR	T	Trough to peak ratio for systolic blood pressure (SBP) measured by ABPM	PPS		LAY_TTPR

* T = Summary Table; F = Figure.

ABPM = ambulatory blood pressure monitoring; ANCOVA = analysis of covariance; DBP = diastolic blood pressure; FAS = Full Analysis Set; MCP-Mod = Multiple Comparison Procedure – Modeling; OBPM = automated office blood pressure measurement; PPS = Per-Protocol Set; SBP = systolic blood pressure; SiDBP = sitting diastolic blood pressure; SiSBP = sitting systolic blood pressure.

ABPM analyses are based on the subset of the PPS described in Section 5.5.

Age category: < 65 vs ≥ 65 years.

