- The areas under the DBP and SBP curves are 8,640,870 and 12,956,970 mmHg sec, respectively. Dividing both areas by the time span of 88,500 seconds gives a 24-hour means of 97.6 and 146.4 mmHg, respectively.
- The mean daytime DBP = $(3,705,300 + 801,570) / (37,860 + 7440) = 99.5$ mHg.
- The mean daytime SBP = $(5,224,530 + 1,295,970) / (37,860 + 7440) = 143.9$ mmHg.
- The mean night time DBP = $1,411,200 / 18,000 = 78.4$ mmHg.
- The mean night time SBP = $2,438,100 / 18,000 = 135.5$ mmHg.

Note that measurements between 21:00 on the first day and 01:00 on the second day (limits excluded) and between 06:00 and 09:00 on the second day (limits excluded) are included in the calculation of the 24-hour means, but not in the calculation of the daytime or night time means.

[figure not shown]
C. Calculation of trough-peak ratios based on ABPM

The figure below shows the mean diastolic ABPM by hour for a single treatment group at baseline (black) and Week 8 (red).

- The mean diastolic ABPM at trough is the average difference between the curves between 20 and 24 hours (circles)
- The mean diastolic ABPM at peak is the average difference between the curves between 2 and 6 hours (circles)

The trough to peak ratio for DBP based on ABPM is the ratio of the two.

The trough to peak ratio for SBP based on ABPM is calculated similarly.

D. Document history

Version	Effective Date	Reason
1.0	8 May 2017	New
2.0	15 May 2017	Update pre-unblinding

STATISTICAL ANALYSIS PLAN
FOR SAMPLE SIZE RE-ESTIMATION
STUDY AC-080A201

Purpose of Analysis	Blinded Sample Size Re-estimation
Investigational Drug	ACT-132577
Protocol Number	AC-080A201
Idorsia Document Number	D-17.086
Document Status/Version Number	Final Version 2
Date	3 November 2017
Author	[REDACTED], Expert Statistician
Reviewers	[REDACTED] Senior Expert Statistician [REDACTED], VP Science Medical Expert

Property of Idorsia Pharmaceuticals Ltd

Confidential

May not be used, divulged, published or otherwise disclosed
without the consent of Idorsia Pharmaceuticals Ltd

TABLE OF CONTENTS

LIST OF ABBREVIATIONS AND ACRONYMS	4
1 INTRODUCTION.....	5
2 STUDY DESIGN AND FLOW	5
2.1 Study design	5
2.2 Study visit and assessment schedule	6
3 OBJECTIVES	9
4 CHANGES OR CLARIFICATIONS TO ANALYSES PLANNED IN THE STUDY PROTOCOL	9
5 DEFINITIONS OF VARIABLES	9
5.1 Screening failures	9
5.2 Subject characteristics	9
5.3 Study treatment exposure and compliance	9
5.4 Study discontinuation	9
5.5 Efficacy variables	9

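### The trough-to-peak ratio is corrected for baseline within each arm but not for placebo; tabulate placebo-subtracted trough and peak differences in mmHg beside it

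*SAP*

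**What the plan says.** SAP 5.5.2 defines the DBP ratio at treatment-group level and states that it "will be corrected for baseline according to the following steps". ABPM readings are averaged by hour after drug intake for each patient and then for each arm. For each hour and arm "the difference in mean ABPM-DBP between Week 8 (Visit 7 Part 1) and baseline (Visit 4 Part 1) will be obtained". The ratio is the average of the five differences at hours 20–24 over the average of the five at hours 2–6.

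Appendix C illustrates this with one arm and two curves, baseline and Week 8: "The trough to peak ratio for DBP based on ABPM is the ratio of the two". SAP 5.5.3 treats systolic pressure alike: "The trough to peak ratio for SBP will be derived on treatment group level based on the time course of ABPM".

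SAP 4.1.2 declares the move from subject-level to group-level ratios, "following the reasoning in recent FDA reviews such as FDA 2007", and replaces the protocol's ANCOVA of log ratios with descriptive statistics. On display, SAP 10.7 adds: "Additionally, the Week 8 minus baseline difference will be plotted vs time". SAP 13.7 lists the matching figure, "Difference in mean diastolic blood pressure (DBP) per hour as measured by ABPM". In summary tables "the order of the treatment groups is: placebo, ACT-132577 5 mg" and so on, so placebo gets its own row or column.

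No section subtracts placebo from the trough and peak windows. SAP 10.7 says in general terms that secondary variables use 95% CIs, but gives no interval method for this ratio.

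**The concern.** A trough-to-peak ratio is read as a property of the drug: how much of the peak effect remains at the end of the dosing interval. Subtracting baseline removes the usual daily pattern and whatever happened during run-in. It does not remove change after randomization, such as regression to the mean, season or familiarity with the device. Only the concurrent placebo arm can remove that.

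What is left enters both numerator and denominator. A given non-drug change moves the ratio more in arms with a small peak effect. Doses with the same true ratio could therefore show different ratios, and the planned table has no number that separates the two explanations. The stake is how one secondary descriptive endpoint is read. No test or decision rule depends on it.

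**Working it through.** **The plan's own figure.** The documents state no trough-to-peak ratio, precision or ABPM effect, so there is nothing to reproduce. Every input below that is not attributed to a document is an assumption.

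**Formula.** Let T and P be the drug effects against placebo at trough and peak, and pt and pp the placebo-arm changes in the same windows.

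- Planned ratio in an active arm: (T + pt)/(P + pp)
- Drug ratio: T/P

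If pt = pp = p, the two agree when p = 0 or T = P. More generally they agree when the placebo change has the same trough/peak ratio as the drug.

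**Equal placebo change, P = −4 mmHg.**

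| True T/P | p = +1 | p = 0 | p = −1 | p = −2 |
|---|---|---|---|---|
| 0.50 (T = −2) | −1/−3 = 0.33 | 0.50 | −3/−5 = 0.60 | −4/−6 = 0.67 |
| 0.75 (T = −3) | −2/−3 = 0.67 | 0.75 | −4/−5 = 0.80 | −5/−6 = 0.83 |

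SAP 10.6.3 assumes a placebo change of −4 mmHg for office SiDBP. Used as a proxy, this gives (−2 − 4)/(−4 − 4) = 0.75 for a true 0.50. ABPM may change much less.

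**Same true ratio of 0.50, different peak effects.**

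| P (mmHg) | −1 | −2 | −4 | −5 |
|---|---|---|---|---|
| p = −1 | 0.75 | 0.67 | 0.60 | 0.58 |
| p = −2 | 0.83 | 0.75 | 0.67 | 0.64 |

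**Unequal placebo change (T = −2, P = −4).** With pt = −1 and pp = −3: −3/−7 = 0.43. With pt = −3 and pp = −1: −5/−5 = 1.00. The error can go either way.

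**Usable subjects.** SAP 4.2 gives 490 randomized, or 490/6 ≈ 82 per arm. SAP 5.5 expects fewer than 50% of subjects in the ABPM subset, so at most about 41. If that is half of a PPS of 80% (the sample size re-estimation SAP anticipates at least 80%), 82 × 0.8 × 0.5 ≈ 32.

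**Precision of a placebo-subtracted difference.** SE = SD × √(2/n), with SD 7–9 mmHg borrowed from the office SiDBP planning.

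- SD 7, n = 41: 7 × √(2/41) = 1.5 mmHg; 95% CI about ±3.0
- SD 9, n = 32: 9 × √(2/32) = 2.25 mmHg; 95% CI about ±4.4

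**Would a placebo-subtracted ratio be better?** Simulation: 400,000 draws per setting, normal arm means, n = 32, trough-peak correlation 0.5, p = −1 unless stated. Paired values are for SD 7 and SD 9.

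- P = −4, true 0.50: the subtracted ratio's 95% range is about −0.8 to 1.8, or −2.0 to 3.0. The planned ratio is closer to 0.50 in 64–70% of trials at p = −1 or −2.
- Showing the subtracted ratio only when the peak difference is significant: shown in 7–9% of trials at P = −1, 14–21% at −2, and 63% or 43% at −4.
- That rule selects inflated peaks. For a true −4 the mean peak among passing trials is −5.1 or −6.1 mmHg.
- The selection biases the ratio. Among passing trials a true 1.0 at P = −2 has a median of about 0.73 or 0.67, and a true 0.80 at P = −4 has 0.74 or 0.70. The planned ratio's median in the second case is 0.84 without selection.

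The differences in mmHg need no division and no selection.

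**The case against.** The choice is deliberate, recorded before unblinding and tied to a cited regulatory review that cannot be checked here. Baseline ABPM is recorded on placebo after a run-in of 4 to 6 weeks (Protocol 3.1 and 8.1.4), which Protocol 3.2 intends to limit regression to the mean. A true ratio of 0.50 has no source. With a half-life near 44 h (Protocol 1.2.1), concentration from 4 h to 22 h falls to 2^(−18/44) ≈ 0.75 of its value. If effect follows concentration, the true ratio is nearer 0.75 and the distortion at p = −1 or −2 is halved. Placebo-controlled ABPM results are also planned: the 24-hour, daytime and night-time ANCOVAs, besides the hourly plots by arm.

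Most of this stands, and it keeps the point small. It does not remove it. Run-in cannot remove change after randomization, and for office SiDBP the SAP itself assumes a placebo change of −4 mmHg from a baseline taken after that run-in. The plots allow a comparison by eye only. The ANCOVA windows are not the ratio's windows: with dosing between 07:00 and 10:00, hours 2–6 are a small part of the 09:00–21:00 daytime window, and hours 20–24 overlap 01:00–06:00 only in part.

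A reader might infer that the planned ratios are known to be biased upward, or that a placebo-subtracted ratio should replace them. The documents support neither. They give no ABPM placebo change, and at the expected numbers the subtracted ratio is usually further from the truth.

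**Conclusion.** The point holds in a limited form. As defined in SAP 5.5.2, 5.5.3 and Appendix C, each active arm's ratio is (T + pt)/(P + pp), so it is not placebo-corrected. That is algebra and needs no assumption. The size is not known: it is zero if placebo ABPM does not change, and smaller the nearer the true ratio is to 1. Under the illustrative inputs (P = −4 mmHg, placebo fall of 1–2 mmHg), a true 0.50 reads 0.60–0.67 and a true 0.75 reads 0.80–0.83.

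The endpoint is descriptive and SAP 10.1 controls alpha only for the main analysis, so the primary conclusion is untouched. The gap is a missing pair of placebo-controlled numbers for the two windows the ratio uses. This is an improvement to consider, held with medium confidence because no ABPM input is documented.

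**What to change.** Keep the planned ratio and its windows. In SAP 5.5.2, 5.5.3, 10.7, 10.8 and Appendix C, add for each ACT-132577 dose and lisinopril, and for both DBP and SBP:

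- the Week 8 minus baseline mean difference over hours 20–24, active arm minus placebo, in mmHg with a 95% CI;
- the same over hours 2–6;
- a table note that the planned ratio is corrected for baseline but not for placebo.

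A bootstrap that resamples subjects within arm, keeping each subject's baseline and Week 8 profiles together, gives the intervals without changing the hourly group-level definition.

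Do not make a placebo-subtracted ratio a headline result, and do not make its display depend on a significant peak difference. If it is shown, show it for every active arm with a Fieller or subject-level bootstrap interval, including wide or unbounded ones.

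The cost is a few table rows and little programming, since the hourly means are already derived. The intervals will be wide (SE about 1.5–2.3 mmHg under the assumptions above). The rows share one placebo curve, so a chance error in it moves all doses together. They also inherit the selection into the ABPM subset of the PPS, which subtraction does not repair.
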